6.1.6 Randomization Procedures

The investigator or investigator's designee will access the IVRS/IWRS at Screening to obtain the subject's study number. The investigator or the investigator's designee will utilize the IVRS/IWRS to enter the subject into the Placebo Run-in Phase. The IVRS/IWRS will also be used to randomize the subject into the DB Phase and later the Withdrawal Phase. The DB Phase randomization will be stratified by age (Tanner stage <3, ≥ 3), weight (≥ 25 to < 50 kg, ≥ 50 kg), and race (non-Black, Black). Enrollment caps will also be applied to randomization to ensure a percentage of subjects with secondary hypertension of approximately 20% and to ensure that no more than $\approx 25\%$ of subjects are post-renal transplant patients and no more than $\approx 80\%$ of subjects

weigh greater than or equal to 50 kg at Baseline Randomization for the Withdrawal Phase will be stratified by the treatment received in the DB Phase (ie, AZM-L, AZM-M, or AZM-H or losartan).

6.2 Justification for Study Design, Dose, and Endpoints

6.2.1 Patient Selection

In the US, the overall prevalence of childhood hypertension is 2% to 5%, making it one of the most common chronic diseases of childhood [5]. Similarly, the overall prevalence of pediatric hypertension in European countries generally ranges between 2% to 4% [6-9]. The causes of pediatric hypertension are diverse and age dependent: in infants and children, hypertension is usually secondary to an underlying disorder, most commonly renal parenchymal or renovascular disease [10-13]. In older children and adolescents, primary hypertension is more prevalent and often associated with overweight or obesity [14-17].

The targeted percentage of subjects with secondary hypertension randomized in this study will be at least 20%. Accordingly, many subjects are anticipated to have hypertension associated with underlying CKD. However, subjects with severe renal impairment (eGFR <30 mL/min/ 1.73 m²) or renal artery stenosis (unilateral or bilateral) will be excluded, as maintenance of adequate eGFR in patients with this condition is highly dependent on AII activity; subjects with hypertension secondary to uncorrected coarctation of the aorta will also be excluded. Subjects who are renal transplant patients will be allowed to enroll as long as renal graft function and immunosuppressive therapy (which alter BP) are stable. To maintain generalizability of the study results, the percentage of renal transplant patients will be monitored via IVRS/IWRS and a cap will be applied to maintain enrollment below ≈25%.

6.2.2 Dose Selection for AZM

Pharmacokinetic modeling and simulation of data from study TAK-491_109 [21] in pediatric subjects (6 to <17 years) indicate that the 20, 40, and 80 mg doses of AZM, each of which was demonstrated to be safe and effective in phase 3 trials of hypertensive adult patients, provide similar levels of exposure in children who weighed 50 to 100 kg as has been observed in adults. The 20 mg and 80 mg doses as well as a 10 mg dose will be evaluated in the higher weight group of this study (ie, ≥50 kg). A dose range that includes the 10, 20, and 40 mg strengths of AZM will be administered to lower weight subjects (ie, 25 to <50 kg) to maintain similar exposures in these children as was observed at the 20 to 80 mg doses in adults.

In order to ensure that a sufficient number of subjects in both weight categories are enrolled, the proportion of subjects ≥50 kg will be monitored via IVRS/IWRS and a cap will be applied to maintain enrollment of these subjects to below ≈80%.

6.2.3 Use of Placebo

Exposure to placebo will be restricted to the Washout/Placebo Run-in and the Withdrawal Phase. The standard duration of the Washout/Placebo Run-in is 2 weeks, although subjects whose BP remains controlled (ie, seDBP and seSBP <95th percentile or <90th percentile if chronic renal

CONFIDENTIAL

disease, diabetes, heart failure or hypertensive target organ damage is present) after the washout and therefore do not qualify for randomization, may have the washout extended in 1-week increments for up to 2 additional weeks. The purpose of the Washout/Placebo Run-in is to establish a treatment-free baseline BP, as well as to reduce the influence of the placebo effect, prior to initiation of double-blind treatment. In addition, the run-in allows the opportunity to assess subject compliance with study medication (ie, placebo), and subjects who are not sufficiently compliant with single-blind placebo (ie, >130% or <70%) will not qualify for randomization.

In the Withdrawal Phase, half of the subjects will be randomized to receive 2 weeks of placebo treatment, while the other half will continue their current active treatment. The purpose of the randomized, placebo-controlled withdrawal is to allow for direct comparison between AZM and placebo, thereby facilitating estimation of a placebo-adjusted treatment effect for AZM.

Together, the maximum cumulative duration in which an uncontrolled subject may be untreated is 4 weeks, which will be divided into 2 non-consecutive phases. This maximum duration of exposure to placebo is regarded as safe based on meta-analysis of AE and SAE data from 10 pediatric hypertension trials that incorporated a 2 to 4 week, placebo treatment period [22]. Similarly, meta-analysis of safety data from adult hypertension trials indicated that short-term exposure to placebo (usually 4 to 8 weeks) did not increase risk of cardiovascular events relative to active therapy [23]. At any point of the study, a subject whose BP becomes elevated to greater than 15/10 mm Hg above the 99th percentile and is confirmed on repeat test will be discontinued.

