6.0 STUDY DESIGN AND DESCRIPTION

6.1 Study Design

AR14.001 is a global phase 3, efficacy and safety study of AZM in children aged 6 to <18 years with primary or secondary hypertension. At least 213 subjects will participate in a 6-week, double-blind, randomized, treatment phase (DB Phase), followed by a 2-week, double-blind, randomized placebo-controlled withdrawal (Withdrawal Phase). In the DB Phase, subjects will be randomized (1:1:1:1) with AZM (high, intermediate, or low) using 4 doses (10, 20, 40, and 80 mg) or losartan. In the Withdrawal Phase, subjects will be randomized (1:1) to continue taking their previously assigned active treatment or to be switched to placebo. This study also includes a 44-week, OL extension (OL Phase) in which all subjects will receive AZM and other antihypertensive medications (if needed) according to a titrate-to-target BP algorithm. The study will be conducted at approximately 120 sites. BP will be assessed in the clinic throughout the study, and subjects may also participate in a 24-hour ABPM procedure at Baseline, at the end the DB Phase and at the end of the OL Phase.

A schematic of the study design is included as [Figure 6.a](#). A schedule of study procedures is listed in [Section 9.b](#).

Figure 6.a Schematic of Study Design

AZM-L=low-dose AZM, AZM-M=intermediate-dose AZM, AZM-H=high-dose AZM, RZ=Randomization, D=Day, W=Week.

(a) β -blocker use should be tapered off gradually during the first week of the washout. If seDBP remains below inclusion criterion #4 (Section 7.1) after the washout, it can be extended in 1-week increments up to 2 times, for a maximum washout of 4 weeks (for currently treated subjects only). Placebo should continue during the extension(s).

(b) All subjects randomized to AZM-M, AZM-H or losartan will be force-titrated at Week 2.

(c) If possible, the procedures planned for Week 8 or 52 should be completed at the time of discontinuation for subjects who prematurely withdraw from double-blind or OL treatment, respectively.

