6.1.2 Screening and Washout/Placebo Run-in Phase

The duration of Screening can be a maximum of 2 weeks. After clinical laboratory tests results are available and eligibility criteria have been verified (except inclusion criterion #4 and exclusion criterion #6 [[Section 7.0](#)]) qualified subjects will enter a 2-week, single-blind, placebo run-in period, with the first dose to be dispensed in the clinic. For currently treated subjects, the placebo run-in will also serve as a washout period, and antihypertensive medications will be discontinued at Visit 2; however, β -blockers (BBs) should be tapered off gradually during the first week of the washout. Therefore, all currently treated subjects will have a minimum of 7 drug-free days prior to their qualifying clinic seDBP assessment and subsequent randomization.

Qualified **currently treated subjects** will be eligible for randomization after the Washout/Placebo Run-in if their seDBP is \geq 95th percentile for age, gender, and height or \geq 90th percentile by age, gender, height if chronic renal disease, diabetes, heart failure or hypertensive target organ damage is present (ie, inclusion criterion #4 is satisfied) according to percentiles published in the US NHLBI Fourth Report on the Diagnosis, Evaluation, and Treatment of High Blood Pressure in Children and Adolescents [5]. If a subject's seDBP remains $<$ 95th percentile for age, gender, and height or $<$ 90th percentile by age, gender, height if chronic renal disease, diabetes, heart failure or hypertensive target organ damage is present after the Washout/Placebo Run-in (ie, does not satisfy inclusion criterion #4), the washout may be extended in 1 week increments up to 2 times, for a maximum possible washout of 4 weeks, as long as seSBP also remains below this threshold. Placebo should be continued during the extension(s). Subjects whose seDBP remains below the entry criteria after the extensions will not be eligible for randomization to the double-blind treatment phase and shall be discontinued from the study as a run-in failure and referred back to their treating physicians to resume appropriate antihypertensive treatment.

Qualified **currently untreated subjects** will have their BP assessed on 3 occasions prior to randomization including Day -1 (or Day 1 for subjects not participating in ABPM). (The initial 2 assessments may occur at Visit 1/Day -28 and Visit 2/Day -14 or as determined by the

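### Protocol section 6.2.3 calls 4 weeks the maximum placebo exposure, but a child whose washout is extended twice can receive 6 weeks

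*Protocol*

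**What the plan says.** Section 6.2.3 restricts placebo to the Washout/Placebo Run-in and the Withdrawal Phase. It sets the standard run-in at 2 weeks and allows up to two extra weeks for subjects whose pressures are still below threshold. For the Withdrawal Phase it says that "half of the subjects will be randomized to receive 2 weeks of placebo treatment".

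It then draws the two phases together: "the maximum cumulative duration in which an uncontrolled subject may be untreated is 4 weeks". The following sentence takes up that figure as "This maximum duration of exposure to placebo is regarded as safe based on meta-analysis of AE and SAE data from 10 pediatric hypertension trials", and describes those trials as having a placebo period of 2 to 4 weeks. Adult data, usually covering 4 to 8 weeks, are cited next. The section closes with the rule that a child whose pressure is confirmed at more than 15/10 mm Hg above the 99th percentile is discontinued.

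The extension rule is in section 6.1.2. Currently treated subjects may be extended by one week, twice, "for a maximum possible washout of 4 weeks, as long as seSBP also remains below this threshold", and they remain on placebo meanwhile. Only those still below the seDBP entry level after the extensions are excluded. Section 6.1 sets the later step: "In the Withdrawal Phase, subjects will be randomized (1:1) to continue taking their previously assigned active treatment or to be switched to placebo". Sections 6.1.6 and 8.3 stratify that second randomization by double-blind treatment, with no restriction by washout length.

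**The concern.** The two sentences in section 6.2.3 describe different quantities. Time untreated while uncontrolled leaves out the extension weeks, because extensions are open only to children below threshold. Exposure to placebo includes them, because placebo continues through each extension. Carrying the 4-week figure from the first quantity to the second understates the maximum, and no sentence in the protocol states the larger total.

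This sentence is the protocol's stated safety basis for placebo in children. A reader who takes it at face value, such as an ethics committee member, may take 4 weeks as the ceiling.

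A related gap concerns the condition that makes the extra weeks acceptable, namely that both pressures are below threshold. Figure 6.a note (a), section 8.1.3 and Table 9.b note (g) state the extension rule on seDBP alone, as does note (a) to Table A in the SAP. Read literally, those four places would let a child with low seDBP but high seSBP stay on placebo. That is contrary to the synopsis and to sections 6.1.2, 6.1.4.1, 6.2.3, 9.3.3.2 and 9.3.4.1.

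**Working it through.** **Inputs**
- Standard run-in on placebo: 14 days (section 6.2.3).
- Each extension: 7 days on placebo, at most two, currently treated subjects only (section 6.1.2).
- Double-blind active treatment: 42 days (section 6.1).
- Withdrawal placebo: 14 days, assigned 1:1 (sections 6.1 and 6.2.3).
- Visit windows: unextended run-in 14 ± 5 days; Weeks 6 and 8 each ± 2 days (Table 9.b and its note (e)).

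**The plan's own figure.** Run-in + withdrawal = 14 + 14 = 28 days, or 4 weeks. It reproduces.

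**Total placebo by number of extensions (nominal).** Total = 14 + 7k + 14, where k is the number of extensions. The share is the total divided by the time from the start of run-in to Week 8, which is 14 + 7k + 42 + 14.

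| Extensions | Before randomization | Withdrawal | Total placebo | Against 28 days | Share of time |
|---|---|---|---|---|---|
| 0 | 14 | 14 | 28 days (4 weeks) | none | 28/70 = 40% |
| 1 | 21 | 14 | 35 days (5 weeks) | +7, 25% more | 35/77 = 45% |
| 2 | 28 | 14 | 42 days (6 weeks) | +14, 50% more | 42/84 = 50% |

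**With visit windows.** Week 6 two days early and Week 8 two days late make the withdrawal block 14 + 2 + 2 = 18 days.
- Twice-extended child: 28 + 18 = 46 days.
- Unextended child: (14 + 5) + 18 = 37 days.

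**Longest unbroken block.** 28 days before randomization, then 42 days of active treatment, then 14 days (18 with windows).

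**Is the 4-week limit for uncontrolled subjects broken by extension?** In a twice-extended child who then qualifies, the last below-threshold visit is one week before the qualifying visit. Placebo time after that visit is 7 + 14 = 21 days nominal, or 7 + 18 = 25 days with windows. Both are under 28, so the extensions do not breach that limit.

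**The case against.** The strongest reply is that 4 weeks is no arithmetic error. It equals 2 + 2, and the word that opens the disputed sentence points back to a statement limited to uncontrolled subjects. The extension weeks and the withdrawal weeks are both disclosed in section 6.2.3, so a careful reader can add them up. The below-threshold condition, the adult data and the stopping rule are there as well. All of this stands, and it limits the point to wording. It does not make the sentence correct. The sentence speaks of placebo exposure, in a section about the use of placebo that has just described the extensions, and the total it implies is two weeks short.

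Three stronger readings are tempting, and the documents support none of them.
- *Children may be left uncontrolled and untreated for 6 weeks.* Under section 6.1.2, extensions require both pressures to be below threshold, and the 21 to 25 days calculated above stay within the stated limit.
- *Six weeks exceeds what the cited pediatric trials cover.* Each block here is within 2 to 4 weeks. The documents do not show whether children in those trials had further placebo, such as a run-in, so a comparison of cumulative exposure cannot be made.
- *Inclusion criterion 10 is wrong because it mentions only 4 weeks.* It is expressly about the time before randomization and is correct as written.

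It is also fair to say that the seDBP-only statements are abbreviations, and that the visit sections where the decision is made carry the full rule. Even so, the schedule footnote and the dosing section are places that a site may consult on their own.

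**Conclusion.** The point holds as a correction to the stated safety justification. Four weeks is right, nominally, for uncontrolled subjects. Maximum total placebo exposure is 6 weeks nominal: up to 4 weeks before randomization and 2 weeks in withdrawal. Windows take this to about 46 days for a twice-extended child and 37 days for an unextended one; the point does not depend on them.

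It assumes that an extended child who qualifies goes on to the second randomization like any other, and nothing in sections 6.1.6 or 8.3 says otherwise. About half of the extended children who reach the Withdrawal Phase would be switched to placebo. How many children are extended is not given, so the number affected is unknown.

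Nothing here shows that the design is unsafe, and sample size, power, type 1 error and the analyses are untouched. This is a low-severity change worth making because the corrected figure is the less favourable one.

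**What to change.** In section 6.2.3, give the two quantities separately:
- 4 weeks (nominal) as the limit on untreated time for uncontrolled subjects;
- 6 weeks (nominal, a few days more with visit windows) as the maximum total placebo exposure, at most 4 weeks of it consecutive and the two blocks separated by 6 weeks of active treatment.

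Rest the 6 weeks on the support already in the section: seDBP and seSBP both below threshold during extensions, each block within 2 to 4 weeks, the adult data at 4 to 8 weeks, and the 15/10 mm Hg stopping rule.

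Add the seSBP condition, as worded in section 6.1.2, to Figure 6.a note (a), section 8.1.3, Table 9.b note (g) and SAP Table A note (a).

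The cost is one or two sentences and a short clause in four places. No rule, dose, endpoint or analysis changes; the only drawback is a less favourable stated figure.

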6.2.4 Selection of Active Comparator

This study will evaluate the efficacy and safety of AZM relative to the active comparator losartan, which belongs to the ARB class and is approved for use in the pediatric population aged 6 years and older. The losartan tablets administered in the present study (ie, 25 to 50 mg in subjects <50 kg and 50 to 100 mg in patients \geq 50 kg) are established as safe and effective in children \geq 6 years of age [24,25].

6.2.5 Endpoint Selection

In a large meta-analysis of observational studies (61 studies, >1 million subjects) by Lewington et al, a continuous relationship between BP and cardiovascular risk was observed in adults throughout the normal range of usual BP to at least 115/75 mm Hg [26], such that each 10 mm Hg rise in SBP or 5 mm Hg rise in DBP was associated with a 40% increased risk of death by stroke and a 30% increased risk of death from ischemic heart disease. Moreover, interventional outcomes studies completed in adults have shown consistently that lowering BP in patients with hypertension reduces risk of cardiovascular events. Risk reduction is observed during treatment with various agents from multiple drug classes with disparate mechanisms of action, suggesting that benefit is derived largely from the decrease in BP rather than any particular property of a given drug.

While large interventional outcomes studies are lacking in the pediatric population, evidence to support an association between BP and cardiovascular risk is available from pathology and

biomarker studies. BP assessments completed in children and young adults either directly [27] or by estimation [28] correlated with atherosclerotic burden in the coronary arteries, and childhood hypertension has been shown to predict increased carotid intima media thickness in adulthood [29]. Similarly, the prevalence of left ventricular hypertrophy was shown to increase in adolescents as hypertension severity increases [30,31]. In addition to these relationships, a diagnosis of hypertension in childhood was shown to be associated with a significantly increased risk of premature death from endogenous causes [32].

The primary efficacy variable of the study is the change in trough clinic seDBP. The underlying pathophysiology associated with elevated BP in children is often different than in adults (ie, increased vascular resistance versus reduced arterial compliance); therefore, elevated DBP (or both elevated DBP and SBP) is more common in the pediatric hypertensive population, especially when compared with elderly adults who often present with isolated systolic hypertension due to age-related atherosclerotic stiffening of the arteries [33]. DBP is also associated with less physiological variability in children than SBP and this attribute may improve the ability to detect meaningful differences between doses and treatments [34]. The pathophysiology of pediatric hypertension, as well as the smaller intra-individual variability of DBP, justify selection of DBP as the primary endpoint; however, change in seSBP will also be evaluated thoroughly.

As described in [Section 13.3](#), the sample size of this study (N=52/arm) provides >80% power (at the 0.05 significance level) to detect a treatment difference between AZM and placebo of 4.5 mm Hg in DBP. A treatment effect of this magnitude is considered clinically meaningful based on evidence from adult and pediatric studies summarized above, and as reflected in published treatment guidelines. According to European Society of Hypertension (ESH) and NHLBI guidelines for treatment of pediatric hypertension, a reduction in DBP of 4 to 5 mm Hg in the age range of subjects being recruited in this study corresponds to a shift from the 95th percentile (ie, the threshold for a hypertension diagnosis) to the 90th percentile (ie, conventional BP target) depending on age, gender, and height.

Throughout the study, clinic BP will be assessed with a sponsor-provided automated (oscillometric) device that has been validated for use in pediatric patients. Use of an automated device provides the additional advantage of reducing the impact of observer bias, which is inherently associated with manual measurements.

Changes in various parameters of DBP and SBP by ABPM will be evaluated as exploratory endpoints in this study. The utility of ABPM in adult hypertension is well established as both a diagnostic and prognostic tool [34-38]. In addition, ABPM is gaining acceptance in clinical practice as a useful diagnostic tool in children and adolescents [39,40]. For example, ambulatory BP readings may be useful in evaluating or confirming that BP control is maintained throughout the day in children with target organ damage, or to differentiate between primary and secondary forms of hypertension, which may exhibit different diurnal profiles [40,41]. Advantages of ABPM in the clinical trial setting include the ability to evaluate BP changes throughout the dosing interval and a reduced susceptibility to observer bias and placebo effect.

6.2.6 BP Targets in the Open-Label Phase

During the OL Phase, subjects will have their medication adjusted to maintain a BP target <90th percentile for age, gender, and height, which is consistent with ESH 2009 guidelines for management of hypertension in pediatric patients [39].

For subjects with CKD (eGFR <60 mL/min/1.73 m²), antihypertensive therapy may be managed at the investigator's discretion to achieve greater BP reduction. While the US NHLBI guidelines for pediatric hypertension do not recommend a target lower than the 90th percentile for subjects with CKD [5], the ESH guidelines suggest children with CKD be treated to a BP target <75th percentile in the absence of proteinuria and to <50th percentile in the presence of proteinuria. This recommendation is based on evidence from the Effect of Strict Blood Pressure Control and ACE Inhibition on the Progression of Chronic Renal Failure in Pediatric Patients (ESCAPE) trial [41], which was a prospective, randomized comparison of intensive versus conventional BP control in 385 pediatric subjects with CKD. In ESCAPE, randomization to the intensive BP target (ie, 24-hour MAP <50th percentile for age) was associated with a 35% relative risk reduction in progression to ESRD compared with a conventional target (ie, 24-hour MAP between the 50th and 90th percentiles).

